1.2 SCHEMA

Below is an overview of the design of the four RCTs in this study in relation to the three recruitment cycles. The dashed box indicates the primary study (Study 1: ASSIST vs. Delayed Control, combined across Cycles 1 and 2). The other studies are completed within a single cycle: Study 2 (Complexity) in Cycle 1, Study 3 (Lexicality) in Cycle 2, and Study 4 (Intensity) in Cycle 3.

Cycle 1 (Summer 1): COMPLEXITY (simple vs. complex real words).

Group	Condition	wk1	wk2	wk3	wk4	wk5	wk6	wk7
Immediate ASSIST	Simple	T1	8 hrs	8 hrs	T2			T3
	Complex		8 hrs	8 hrs				
Delayed ASSIST	Simple					8 hrs	8 hrs	
	Complex					8 hrs	8 hrs	

Cycle 2 (Summer 2): LEXICALITY (words vs. nonwords).

Group	Condition	wk1	wk2	wk3	wk4	wk5	wk6	wk7
Immediate ASSIST	Real	T1	8 hrs	8 hrs	T2			T3
	Nonsense		8 hrs	8 hrs				
Delayed ASSIST	Real					8 hrs	8 hrs	
	Nonsense					8 hrs	8 hrs	

Cycle 3 (Summer 3): INTENSITY (massed vs. distributed treatment).

Group	Condition	wk1	wk2	wk3	wk4	wk5	wk6	wk7
Massed ASSIST	Immediate	T1	8 hrs	8 hrs	T2			T3
	Delayed					8 hrs	8 hrs	
Distributed ASSIST	Distributed		4 hrs	4 hrs		4 hrs	4 hrs	

STUDY 1 (Primary Objective): ASSIST vs. Delayed Control

Data from Cycles 1 and 2 will be combined (shown in the pink dashed box). Groups (ASSIST, Delayed Control) will be compared at T2.

STUDY 2 (Complexity)

Data from Cycle 1 will be combined across Immediate and Delayed ASSIST. Groups (Simple, Complex) will be compared post treatment. For Immediate ASSIST, pre = T1 and post = T2; for Delayed ASSIST, pre = T2 and post = T3.

[figure not shown]
STUDY 3 (Lexicality)

Data from Cycle 2 will be combined across Immediate and Delayed ASSIST. Groups (Word, Nonword) will be compared post treatment. For Immediate ASSIST, pre = T1 and post = T2; for Delayed ASSIST, pre = T2 and post = T3.

[figure not shown]
STUDY 4 (Intensity)

Data from Cycle 3 will be used to compare groups (Massed, Distributed) at T3. For Massed ASSIST, data will be combined across Immediate and Delayed Massed ASSIST conditions.

[figure not shown]
Study 1 Flow: ASSIST vs. No ASSIST. Combined across two Recruitment Cycles (Cycle 1 and Cycle 2)

[figure not shown]
Study 2 Flow: Simple ASSIST vs. Complex ASSIST). Cycle 1, combined across Immediate and Delayed.

Study 3 Flow: Word ASSIST vs. Nonword ASSIST. Cycle 2, combined across Immediate and Delayed.

Study 4 Flow: Massed ASSIST vs. Distributed ASSIST. Cycle 3.

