1.3 SCHEDULE OF ACTIVITIES

	Pre-screening (Pre-consent)	Visit 1 (up to 3 months before T1)	Visit 2: T1 (week 1)	Visits 3-10 (weeks 2-3)	Visit 11: T2 (week 4)	Visits 12-19 (weeks 5-6)	Visit 20: T3 (week 7)
Recruitment & Phone Screening	X						
Informed Consent		X					
Demographics		X					
Clinical history		X					
Target Selection Questionnaire		X					
SLP diagnosis from 3 SLPs (CAS3SLP)		X					
DEMSS		X					
MaxPT		X					
GFTA		X					
DEAP		X					
SRT		X					
RIAS		X					
OME		X					
Hearing		X					
PPVT		X					
EVT		X					
CELF		X					
CTOPP		X					
Randomization (after final sample has been determined, before T1)		X					
Outcome Evaluation							
Target Repetition Task			X		X		X
TOCS+ Intelligibility			X		X		X
ICS			X		X		X
FOCUS-34			X		X		X
ASSIST or No ASSIST (Delayed Treatment Control group)				X		X	
Adverse Events Reporting (FRS)			X	X	X	X	X

ASSIST = Apraxia of Speech Systematic Integral Stimulation Treatment

CELF = Clinical Evaluation of Language Fundamentals (Semel et al., 2004)

CTOPP = Comprehensive Test of Phonological Processing (Wagner et al., 1999)

DEAP = Diagnostic Evaluation of Articulation and Phonology [Word Inconsistency] (Dodd et al., 2006)

DEMSS = Dynamic Evaluation of Motor Speech Skill (Strand et al., 2013)

EVT = Expressive Vocabulary Test (Williams, 2007)

FOCUS-34 = Focus on Outcomes of Communication Under Six (Thomas-Stonell et al., 2012, 2013a,b)

FRS = Frustration Rating Scale

GFTA = Goldman-Fristoe Test of Articulation (Goldman & Fristoe, 2015)
Hearing = Hearing screen (ASHA, 1997)
ICS = Intelligibility-in-Context Scale (McLeod et al., 2012, 2015)
MaxPT = Maximum Performance Task protocol (Thoonen et al., 1996, 1999)
OME = Oral mechanism examination (Robbins & Klee, 1987)
PPVT = Peabody Picture Vocabulary Test (Dunn & Dunn, 2007)
RIAS = Reynolds Intellectual Assessment Scales [nonverbal subtests] (Reynolds & Kamphaus, 2018)
SRT = Syllable Repetition Task (Shriberg et al., 2009).
TOCS+ = Test of Children's Speech Intelligibility tests (Hodge et al., 2009)

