4.3 JUSTIFICATION FOR INTERVENTION

CAS affects speech communication and thus participation in life, because virtually all social activities depend on speech communication. Children with CAS are at elevated risk for reading and academic challenges, reduced communicative participation, and reduced psychosocial well-being. These effects are long-term. Treatment progress is often slow for CAS, and intensive motor-focused treatment is recommended. Effective treatment for CAS has the potential to improve not only speech communication but also more distal outcomes, such as communicative participation.

ASSIST is delivered over 32 sessions for a total of 16 hours over 4 weeks (Study 4, Distributed group) or 2 weeks (all other groups). The amount is comparable to previous studies with other treatment approaches. ASSIST is delivered individually in a pull-out model in the context of a day camp setting. This context was chosen to minimize missed sessions and to provide a naturalistic supportive social environment. If at least 14 sessions (7 hours) are available, data are evaluable. All data are valuable given the current lack of RCT level evidence for integral stimulation treatments for CAS.

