6.4 STUDY INTERVENTION/EXPERIMENTAL MANIPULATION ADHERENCE

The Summer Camp setting is designed to maximize attendance for intervention sessions. Attendance is facilitated by stating the fixed dates of the study in advance (including on recruitment materials), by providing a detailed week-by-week camp schedule before the start of camp, and by daily contact with families during drop-off and pick-up. Absences will be logged daily during camp weeks to enable adjustment for amount of intervention received.

During intervention sessions, adherence to protocol may be reduced due to frustration experienced by the child during difficult treatment tasks. SLPs provide a supportive environment, clear structure with visual supports, and breaks with engaging fun activities to manage the child's behavior and motivation to continue to engage. Tracking sheets are completed each session to log the number of teaching episodes completed, and which targets and utterances are practiced how many times. All sessions are audio- and video-recorded for off-line review. Parents must agree to have their child recorded for data analysis and verification purposes in order to participate (additional uses of recordings are optional).

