9.3 POPULATIONS FOR ANALYSES

Modified Intention-to-Treat (ITT) analysis will be used to statistically analyze the results (i.e., all randomized participants who received at least one session of the intended ASSIST intervention). Per-Protocol analysis will be used in the event that a participant changes intervention condition.

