9.4.2 ANALYSIS OF THE PRIMARY ENDPOINT(S)

The primary endpoint measure is change score from 1 week pre to 1 week post treatment for the populations described above in **Section 9.3, Populations for Analyses**. For perceptual accuracy, at least two independent data analysts (blinded to timepoint, treatment status, condition, and targets) score each target on an ordinal 3-point scale. Mean across the data analysts for each target is then used to compute the mean across treated targets (primary endpoint) and across the full 30-item target set (secondary endpoint 1) for each timepoint (T1, T2, T3). Means are converted to percentage accuracy by dividing means by 2. Finally, difference scores are then computed by subtracting the relevant pre-treatment timepoint from the relevant post-treatment timepoint. These change scores are the primary endpoint variable entered into the analyses described below and will be reported as means with standard error.

To address the effect of ASSIST (the *ASSIST Hypothesis*, Study 1), independent two-sample t-tests will be used to compare change scores (T2 – T1) between the Immediate ASSIST group and the No ASSIST delayed control group (combined sample across Cycles 1 and 2). A separate linear model will be fitted by adjusting for potential effect of study (Cycle 1/Cycle 2) to re-assess the initial efficacy of ASSIST.

To address the effect of complexity (*Simplicity vs. Complexity Hypothesis*, Study 2), independent two-sample t-tests will be used to compare change scores between conditions (i.e., Simple/Complex). Change scores will be based on T2 – T1 for the Immediate ASSIST group and T3 – T2 for the Delayed ASSIST group. Separate linear models will be fitted by adjusting for potential effect of ASSIST delivery time (Immediate/Delayed) to re-assess the effect of complexity.

To address the effect of lexicity (*Word vs. Nonword Hypothesis*, Study 3), independent two-sample t-tests will be used to compare change scores between conditions (i.e., Word/Nonword). Change scores will be based on T2 – T1 for the Immediate ASSIST group and T3 – T2 for the Delayed ASSIST group. Separate linear models will be fitted by adjusting for potential effect of ASSIST delivery time (Immediate/Delayed) to re-assess the effect of lexicity.

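### The one-session rule in Section 9.3 would exclude a Study 1 control child who completes T2 but never starts ASSIST, so inclusion in that arm can depend on events after the outcome

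*Protocol*

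**What the plan says.** Protocol Section 9.3 calls its population modified intention-to-treat and defines it as "all randomized participants who received at least one session of the intended ASSIST intervention". It adds: "Per-Protocol analysis will be used in the event that a participant changes intervention condition". Section 9.4.2 carries the definition to the main analysis: "The primary endpoint measure is change score from 1 week pre to 1 week post treatment for the populations described above".

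For Study 1, Section 1.2 states: "Groups (ASSIST, Delayed Control) will be compared at T2". Section 9.4.2 specifies two-sample t-tests to "compare change scores (T2 – T1) between the Immediate ASSIST group and the No ASSIST delayed control group", pooling Cycles 1 and 2. The tables in Sections 1.2 and 1.3 place T2 in week 4, Immediate treatment in weeks 2-3 and Delayed treatment in weeks 5-6. For Delayed children, T2 is therefore the pre-treatment visit.

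Neither document gives Study 1 a population of its own, and the SAP text defines no analysis population at all. Section 9.4.3 analyses the secondary endpoints as the primary and rules out imputation.

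**The concern.** In the Immediate arm, the qualifying event (a first session) comes before the Study 1 outcome. In the Delayed arm it can only come after it. Membership of the control group in the analysis thus depends on whether the family stays beyond a visit at which the Study 1 data are already complete.

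If the controls who leave differ in their T1-to-T2 change from those who stay, the comparison loses the protection of randomisation in one arm only. Section 9.2 says the findings will inform effect sizes for Phase 2 and 3 trials, so a shifted estimate would matter even without a false positive result.

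The case is not far-fetched on the protocol's own terms. Section 7.2.1 says randomised children are not replaced whether or not they received any intervention, and Section 5.5.2 asks withdrawing families to return for post-testing so that data are not lost.

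**Working it through.** **1. Order of events (Sections 1.2 and 1.3)**

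| | Immediate arm | Delayed control arm |
|---|---|---|
| First possible ASSIST session | Week 2 | Week 5 |
| Study 1 outcome (T2) | Week 4 | Week 4 |
| Child leaves after T2, before week 5 | Already qualified: kept | Not qualified: excluded |

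A child in either arm who leaves before T2 and is not tested has no T2 score, and no imputation is planned. The asymmetry therefore concerns only children with T2 data.

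**2. The plan's own power figure (Section 9.2, Table 2)**

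Inputs: 20 per group, standardised effect d = 0.909, two-sided alpha 0.05, two-sample t-test. Power comes from the noncentral t distribution with n1 + n2 − 2 degrees of freedom and noncentrality d × √[n1·n2/(n1 + n2)].

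- 20 v 20: 0.909 × √(400/40) = 2.87 on 38 df, giving 79.99%. The plan states 80%.
- At 19, 18, 17, 16 and 15 per group: 77.8, 75.5, 72.9, 70.1 and 67.1%. The plan states 77, 75, 72, 70 and 67%. The table reproduces to within a point.

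**3. Effect of losing k of 20 controls after T2**

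The documents give no rate for this interval, so k is an assumption. Change scores are taken as normal with SD 1. Power uses the formula above with 20 v (20 − k); for k = 2 the noncentrality is 0.909 × √(360/38) = 2.80 on 36 df. Removing k children moves the control mean by the sum of their deviations divided by (20 − k). Shifts and type I error come from 100,000 simulated trials.

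The outer bound removes exactly the k most extreme changers. The moderate case gives each child a liability to leave that correlates 0.5 with the change score.

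| k | Power, loss unrelated to outcome | Outer-bound shift (SD) | Outer-bound type I error | Moderate shift (SD) | Moderate type I error |
|---|---|---|---|---|---|
| 0 | 80.0% | 0 | 5.0% | 0 | 5.0% |
| 1 | 78.9% | 0.10 | 6.9% | 0.05 | 5.4% |
| 2 | 77.7% | 0.18 | 10.0% | 0.09 | 6.1% |
| 3 | 76.4% | 0.26 | 14.5% | not run | not run |

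Relative to the 0.909 SD design effect, the outer-bound shifts are 0.10/0.909 = 11%, 0.18/0.909 = 20% and 0.26/0.909 = 29%. If the lost controls are those with the largest gains, the control mean falls and the ASSIST effect is overstated. If they have the smallest gains, the effect is understated by the same amount. When loss is unrelated to outcome, type I error stays near 5.0% and only the small power loss remains.

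**4. Which endpoints have a score to keep**

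The primary endpoint is accuracy of treated items. Under Section 6.1.1.1.3 a child practises four targets in a session, and a new target enters once all frames of an earlier one are mastered, so the treated items emerge during treatment. A control who never starts has none, and Section 9.4.2 then yields no primary change score for that child. The full 30-item set (SE-1), ICS, FOCUS-34 and TOCS+ (SE-2 to SE-4) are measured at T1 and T2 whether or not treatment starts. The shifts in step 3 therefore describe SE-1 to SE-4 directly, and the primary endpoint once its item set is fixed in advance.

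**The case against.** The strongest reply is that the rule may never operate. Section 7.2.2 expects few withdrawals if any, and Section 5.5.2 counts free treatment as a reason to stay; controls at T2 have yet to receive it. If every control with T2 data starts ASSIST, the rule removes none of them. Selection on the score itself is also implausible: Section 7.2.2 says accuracy is judged only after camp ends, and Section 6.3 says parents are not told the phase, though it concedes they may learn it from the child. Selection on perceived progress remains possible. All this stands. It limits the size of the problem without repairing the rule.

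One might also read the intended intervention as the allocated condition, which would keep these controls. The wording names ASSIST, however, and the control condition has no sessions.

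A reader might infer several stronger points that the documents do not support:

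- *That the primary comparison is already non-randomised, or that valid primary outcomes are being discarded.* The first depends on a withdrawal that may not occur. The second fails because a control who never starts has no primary score as the endpoint is now defined.
- *That the 14-session threshold is a competing analysis set.* Section 4.3 says "If at least 14 sessions (7 hours) are available, data are evaluable", within the justification of the intervention, and Section 4.4 uses 14 sessions to define completion. Neither is stated as an analysis population.
- *That a dose adjustment will distort Study 1.* Section 6.4 says "Absences will be logged daily during camp weeks to enable adjustment for amount of intervention received", but neither Section 9.4 nor the SAP specifies such a model.
- *That crossover is expected and per-protocol will then replace analysis by assignment.* Section 8.4.1 lists receiving the wrong condition as an example of an unanticipated problem, and Section 9.3 does not say whether per-protocol replaces or supplements the main analysis. The fair criticism is that this is left open.

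**Conclusion.** The concern holds as a defect in the written rule, with a conditional effect. As Section 9.3 stands, a control with T1 and T2 data who leaves before the first session is excluded, while an Immediate child leaving at the same time with T2 data is kept.

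The size rests on an assumed number lost and an assumed link between leaving and change. For 1, 2 or 3 of 20 controls the shift is at most 0.10, 0.18 or 0.26 SD in either direction, and about 0.05 and 0.09 SD for 1 and 2 under moderate selection. The power cost is minor: 2.3 points for two children (80.0% to 77.7%).

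This should be fixed. It governs the trial's one primary comparison and is cheap to correct, but the triggering event is expected to be rare and Section 9.2 says the trial is not powered for a definitive effect.

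**What to change.** 1. In Section 9.3 and the SAP, give Study 1 its own population: *Study 1: all randomised children with T1 and T2 scores, analysed in the arm assigned, regardless of sessions received before or after T2.*
2. Pre-specify the items that form the Study 1 primary score at T1 and T2, by the same rule in both arms, drawn from the target sets that Section 6.3 says are created before randomisation. In Cycle 2, where every child has 30 words and 30 nonwords, state which list applies under each assigned condition. SE-1 to SE-4 need no such step.
3. State that analysis by assigned condition is primary in all four studies, and that any per-protocol analysis after a change of condition is supportive only.

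The cost is a few sentences in each document and one decision about items. No new data are needed, because SE-1 already requires the full 30-item set at each timepoint. The item decision needs care: a fixed list may include targets that a child never reached in treatment, which could dilute the effect relative to scoring only practised items. It should be settled before any T2 scores are compared by arm.

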9.4 STATISTICAL ANALYSES

9.4.1 GENERAL APPROACH

Descriptive statistics (e.g., mean, median, standard deviation, skewness, and frequencies) will be computed for all variables to ensure data quality and evaluate assumptions of statistical tests. We will

compare the pre-treatment performance between groups (ASSIST/No-ASSIST, Simple/Complex, Word/Nonword, Massed/Distributed) to assess the success of randomization in producing two comparable groups. Although we do not expect any imbalances between groups, we will adjust for any differences in our subsequent analyses to be sure any treatment effect is not due to potential confounds. For all analyses, we will use Statistical Analysis Software (SAS, v9.4, Cary, N.C.), with two-sided tests under presumed significant level of 0.05.

9.4.2 ANALYSIS OF THE PRIMARY ENDPOINT(S)

The primary endpoint measure is change score from 1 week pre to 1 week post treatment for the populations described above in **Section 9.3, Populations for Analyses**. For perceptual accuracy, at least two independent data analysts (blinded to timepoint, treatment status, condition, and targets) score each target on an ordinal 3-point scale. Mean across the data analysts for each target is then used to compute the mean across treated targets (primary endpoint) and across the full 30-item target set (secondary endpoint 1) for each timepoint (T1, T2, T3). Means are converted to percentage accuracy by dividing means by 2. Finally, difference scores are then computed by subtracting the relevant pre-treatment timepoint from the relevant post-treatment timepoint. These change scores are the primary endpoint variable entered into the analyses described below and will be reported as means with standard error.

To address the effect of ASSIST (the *ASSIST Hypothesis*, Study 1), independent two-sample t-tests will be used to compare change scores (T2 – T1) between the Immediate ASSIST group and the No ASSIST delayed control group (combined sample across Cycles 1 and 2). A separate linear model will be fitted by adjusting for potential effect of study (Cycle 1/Cycle 2) to re-assess the initial efficacy of ASSIST.

To address the effect of complexity (*Simplicity vs. Complexity Hypothesis*, Study 2), independent two-sample t-tests will be used to compare change scores between conditions (i.e., Simple/Complex). Change scores will be based on T2 – T1 for the Immediate ASSIST group and T3 – T2 for the Delayed ASSIST group. Separate linear models will be fitted by adjusting for potential effect of ASSIST delivery time (Immediate/Delayed) to re-assess the effect of complexity.

To address the effect of lexicity (*Word vs. Nonword Hypothesis*, Study 3), independent two-sample t-tests will be used to compare change scores between conditions (i.e., Word/Nonword). Change scores will be based on T2 – T1 for the Immediate ASSIST group and T3 – T2 for the Delayed ASSIST group. Separate linear models will be fitted by adjusting for potential effect of ASSIST delivery time (Immediate/Delayed) to re-assess the effect of lexicity.

To address the effect of intensity (*Massed vs. Distributed Hypothesis*, Study 4), independent two-sample t-tests will be used to compare gain scores (T3 – T1) between the Massed ASSIST group and the Distributed ASSIST group. Because the Massed ASSIST group combines both *Immediate* Massed and *Delayed* Massed groups, no additional models will be fitted by adjusting potential effect of ASSIST delivery time (Immediate/Delayed) to re-assess the effect of intensity.

